### **6.3. Measures to Minimize Bias: Randomization and Blinding**

Blinding and randomization are not applicable. This is an open-label study in which all participants are expected to receive the same dose of ALXN1840.

### **6.4. Study Intervention Compliance**

Participants will receive study intervention directly from the investigator or designee, under medical supervision. The date and time of each dose administered in the clinic will be recorded in the source documents and in the CRF (if the CRF is not the source document). The dose of study intervention and study participant identification will be confirmed at the time of dosing by a member of the study site staff other than the person administering the study intervention. Study site personnel will examine each participant's mouth to ensure that the study intervention was ingested.

For additional information on study intervention compliance and management, refer to the Pharmacy Manual.

### **6.5. Concomitant Therapy**

Any medication or vaccine (including over-the-counter or prescription medicines, vitamins, and/or herbal supplements) or other specific categories of interest) that the participant is receiving from 14 days prior to study enrollment (Day -7) until the end of study visit must be recorded along with:

- Reason for use
- Dates of administration including start and end dates
- Dosage information including dose and frequency

The Medical Monitor should be contacted if there are any questions regarding concomitant and/or prior therapy.

#### **6.5.1. Allowed Medicine and Therapy**

- Paracetamol/acetaminophen at doses of a maximum 1000 mg per day is permitted for use as an exception with the approval of the Investigator.
- As per the ALXN1840 IB, in this study, Investigators should use caution in the co-administration of drugs known to be substrates of cytochromes 2C9 and 2B6 (CYP2C9 and CYP2B6). Common substrates of CYP2C9 include ibuprofen, which is permitted in this study. The Investigator must use ibuprofen with caution during the

conduct of the study, and the ibuprofen dose must not exceed 1200 mg in any 24-hour period. Ibuprofen may only be used with approval of the Investigator.

- Concomitant procedures are not allowed unless medically indicated and/or permitted by Alexion or the Investigator or designee.
- Concomitant medications may be used during the study if deemed medically indicated by the Investigator. The Investigator or designee will notify Alexion of any AEs requiring administration of prescription medication(s) while on study.

### **6.5.2. Disallowed Medicine and Therapy**

Participants must abstain from taking prescription medications within 14 days or 5 half-lives (whichever is longer) of Day -7 or nonprescription drugs (including vitamins and dietary or herbal supplements) within 7 days or 5 half-lives (whichever is longer) before Day -7 and until completion of the follow-up visit, except as described in [Section 6.5.1](#).

## **6.6. Dose Modification**

Asymptomatic elevations of hepatic transaminases and gamma glutamyltransferase have been reported in patients with WD treated with ALXN1840 and have occasionally been seen in ALXN1840 single dose studies in healthy volunteers, and in published data from oncology studies. Liver enzymes will be monitored a minimum of every 3 days throughout the study. In addition, chronic treatment with ALXN1840 may result in anemia, leukopenia or thrombocytopenia due to over-decuppering. As this is the first repeat-dose study to be conducted in healthy participants, complete blood count with platelets will also be monitored a minimum of every 3 days. Ceruloplasmin concentrations will be measured and may be used as appropriate to guide group dosing decisions.

If laboratory tests result in abnormal values, it will be expected that the tests are repeated to confirm those results. Depending on the severity of the abnormal values, laboratory tests may be checked as frequently as daily; it is at the discretion of the Investigator to track abnormal values. Results from non-scheduled safety laboratory assessments must be recorded in the CRF.

Alexion should be notified within 24 hours of any laboratory, vital sign, ECG abnormality or AE that are considered of clinical concern by the Investigator. Investigators must notify Alexion immediately of drug discontinuation. The decision to discontinue drug should not be delayed for causality assessment.

Following dosing of the first group of approximately 6-8 participants, if ceruloplasmin concentrations or AE findings are suggestive of Cu depletion, the SRC ([Section 9.7](#)) may reduce the dose to 15 mg/day for the remainder of the study population.

Dose modification guidelines will be specified as follows.

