**Figure 1: Study Design Schematic**

Participants will be admitted to the CRU on Day -8 and discharged on Day 31.

Participants eligible for the study will be enrolled (assigned a subject number) on Day -7. A Cu- and Mo-controlled diet will be initiated on Day -7 and will be continued through Day 30.

Participants will be administered ALXN1840 at a dose of 30 mg/day on Day 1 through Day 15, with post-treatment period starting at Day 16.

Total intake and total output (I/O) samples for measurement of Cu and Mo will be collected during the baseline (Day -4 through Day -1), treatment (Day 1 through Day 15), and post-treatment periods (Day 16 through Day 31). I/O defines the period in which all intake (food and drink) and all output (urine and feces) will be collected for the measurement of Cu and Mo.

Intensive PK/PD sampling will occur on Day 1 and Day 15. Pre-dose PK/PD samples will be collected on Days 2 (Day 1, Hour 24), 3, 5, 8, 11, and 14. During the post-treatment period, PK/PD samples will be collected on Days 16, 18, 21, 24, 27, and 30.

Abbreviations: CRU = clinical research unit; EOS = end of study; I/O = input/output.

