### 1.3. Schedule of Activities (SoA)

**Table 1: Schedule of Activities**

Study Procedures	Screening a	Check-in b																				EOS or ET c				
	Days	-35 to -9	-8	-7	-6 to -5	-4 to -1	1	2	3	4	5	6-7	8	9-10	11	12-13	14	15	16-17	18	19-20	21-29	30	31	EOS Day 43 ± 2	
Eligibility																										
Informed consent	X																									
Admit to unit		X																								
Discharge from unit																									X d	
Inclusion/exclusion	X	X	X																							
Discuss/document contraception	X	X																								X
Follicle stimulating hormone (post-menopausal females)	X																									
Alcohol test	X	X																								
Urine drug screen	X	X																								
HIV, hepatitis B and C screen	X																									
Study Administration																										
Medical history/demographics e	X	X																								
Physical examination f	X	X																							X	X
Height g , weight, and BMI	X	X																								
Enrollment																										
Enrollment (prior to administration of study intervention)			X																							
Administration of Study Intervention																										
ALXN1840 h						X	X	X	X	X	X	X	X	X	X	X	X	X								
PK Analyses																										
ALXN1840 (total Mo) and PUF Mo PK i						X j	X k	X k		X k		X k		X k		X k	X j	X k	X k			X k,n	X k			
Safety Assessments/Laboratory Analyses																										
Chemistry l , Hematology, Coagulation	X	X			X m		X			X		X		X			X		X			X n		X	X	
Urinalysis	X	X																								X

- g Height at screening only.
- h Study intervention will be administered after an overnight fast (ie, at least 10 hours) at the same time every morning; ALXN1840 is to be administered with 240 mL of water. Participants will remain fasted for a minimum of 2 hours following each dose administration.

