- i Blood samples will be collected pre-dose on dosing days for PK. On Days 1 and 15, intensive blood sampling for PK/PD will occur at the timepoints described in [Table 2](#). Blood samples for PK/PD on Days 16 (Day 15 24-hour time point), 18, 21, 24, 27, and 30 (non-dosing days) will be collected at approximately 0800 and before breakfast.
- j See [Table 2](#) for PK/PD blood sampling and ECG schedules on Days 1 and 15.
- k Procedures will occur pre-dose on Day 1 through Day 15; starting on Day 16, procedure will occur at approximately 0800 and before breakfast
- l Samples for serum chemistry will be obtained following a fast of at least 8 hours at screening, and of at least 6 hours at check-in. In case of dropouts, rechecks, and postdose serum chemistry, participants may not have fasted for 6 or 8 hours before the serum chemistry sample is taken.
- m Day -1 only.
- n Laboratory assessment including chemistry, hematology, and coagulation parameters should be performed on Days 21, 24, and 27; blood sampling for plasma PK (total and PUF Mo) and PD (total and PUF Cu, ceruloplasmin, ceruloplasmin-bound Cu, and LBC) should occur at approximately 0800 or before breakfast on Days 21, 24, and 27.
- o Menstruation check is for women only; Women of childbearing potential should only be enrolled after a negative serum pregnancy test result at screening. Additional urine pregnancy testing will be standard for the protocol unless serum testing is required by site policies, local regulation, or IRBs/IEC ([Section 10.2](#)).
- p A single 15 mL serum sample will be retained for evaluation in the event of an unexpected safety finding; retained samples may be destroyed after completion of the clinical study report
- q Vital signs measurements and ECGs should be performed predose, unless otherwise specified. Vitals signs include body temperature, heart rate, respiratory rate, and systolic and diastolic blood pressure.
- r Cu and Mo controlled meals will be initiated after enrollment (Day -7 breakfast) and continued through Day 30; during this time participants will be strongly encouraged to complete all meals. If a participant is unable to eat 100% of the food, the remaining food will be weighed and reported in the CRF to support Cu/Mo determination as a fraction of total meal ([Table 4](#)).

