concentration cannot distinguish whether the Mo is complexed with Cu and albumin (as in TPC), free active ALXN1840 drug, intermediate hydrolysis products, or molybdate which may be from ALXN1840 hydrolysis. To better characterize the amount of non-TPC bound ALXN1840 and its degradation products, plasma ultrafiltrate Mo (PUF Mo), which represents the free parent drug (ALXN1840), short-lived intermediate hydrolysis products, and molybdate, will be measured. Total Mo and PUF Mo concentrations also include physiologic molybdate concentrations from dietary micronutrient molybdate intake. While it is not feasible to separate and quantify ALXN1840 directly in the plasma, total Mo PK and PUF Mo PK provide surrogate measures to characterize ALXN1840 exposure. To better characterize the ADME of ALXN1840, the PK of both total Mo and PUF Mo will be characterized and described.

Single dose administration of the enterically-coated ALXN1840 under fasted conditions in healthy participants resulted in a peak total Mo concentration, as stable TPC, at approximately 4.54 hours with a half-life of approximately 51 hours. In Study WTX101-HV-106, a 60-mg dose demonstrated a total Mo time to maximum concentration ( $T_{max}$ ) of approximately 6 hours with up to 14% of the total Mo represented as PUF Mo, which also peaked at approximately 6 hours post dose. By 24 hours, PUF Mo had declined to approximately 3-5% of the total Mo. These findings are consistent with results from the Phase 2 Study WTX101-201 in patients with WD. Given the much longer half-life of total Mo, a repeat dose study of 15 days duration will support steady state assessment of ALXN1840 ADME (as measured by total Mo and PUF Mo). In addition, complete collection of Mo over the ALXN1840 treatment period as well as the 15-day terminal elimination period may support a complete assessment of Mo balance for the study.

As this study represents the first repeat dose study in healthy participants, dosing duration will be limited to 15 days. Safety laboratory tests will be monitored at least every 3 days with individual and cohort stopping criteria in place if significant safety risks are identified. In addition, if findings of Cu depletion or toxicity are identified in the initial study group by Day 18, the dose of ALXN1840 may be reduced to 15 mg/day for the remainder of the enrolled participants.

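### Protocol Sections 4.2 and 6.6 promise safety laboratory tests at least every 3 days, but Table 1 leaves a 4-day gap during dosing, from Day 11 to Day 15

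*Protocol*

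**What the plan says.** Protocol Section 6.6 (Dose Modification) says "Liver enzymes will be monitored a minimum of every 3 days throughout the study" and, because this is the first repeat-dose study in healthy participants, "complete blood count with platelets will also be monitored a minimum of every 3 days". Section 4.2 makes the general commitment: "Safety laboratory tests will be monitored at least every 3 days with individual and cohort stopping criteria in place".

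The draws themselves are set in Table 1, in the row for chemistry, "Hematology, Coagulation". After screening, that row with its footnotes gives Days -8, -1, 2, 5, 8, 11, 15, 18, 21, 24, 27, 31 and the end-of-study (EOS) visit on Day 43 ± 2. Footnote m limits the Day -4 to -1 column to Day -1. Footnote n fills in the Day 21 to 29 column: "Laboratory assessment including chemistry, hematology, and coagulation parameters should be performed on Days 21, 24, and 27".

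Blood is already drawn for other purposes on the days that matter here. The text under Figure 1 says "Pre-dose PK/PD samples will be collected on Days 2 (Day 1, Hour 24), 3, 5, 8, 11, and 14" and "During the post-treatment period, PK/PD samples will be collected on Days 16, 18, 21, 24, 27, and 30".

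**The concern.** The text and the schedule give the site two different instructions. Section 8 of the protocol requires adherence to the Schedule of Activities, yet a site that follows Table 1 exactly misses the interval in Sections 4.2 and 6.6 during dosing.

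The interval is not incidental. Section 4.2 presents it together with the stopping criteria. The individual suspension rules in Section 6.6.1.4 (ALT/AST, hemoglobin, platelets) and the group rules in Section 6.6.1.5 can act only on values that have been drawn. A participant whose results are normal on Day 11 has no further scheduled chemistry or blood count until Day 15. Section 6.6 calls for repeat tests when a value is abnormal, and Section 10.2 lets the Investigator order extra tests, but neither puts a draw on the calendar for a participant who was normal on Day 11.

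**Working it through.** **Reading the row.** In the machine-read copy of Table 1, the day header has 24 columns. Columns 14 to 19 are Day 11, Days 12-13, Day 14, Day 15, Days 16-17 and Day 18. The chemistry row has marks in columns 1, 2, 5, 7, 10, 12, 14, 17 and 19, which are Screening and Days -8, -1 (footnote m), 2, 5, 8, 11, 15 and 18.

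**Checking the alignment.** The PK row has pre-dose marks in columns 7, 8, 10, 12, 14 and 16, matching the listed pre-dose days 2, 3, 5, 8, 11 and 14. Its second footnote-j mark is in column 17, and footnote j names Days 1 and 15. So column 16 is Day 14, blank for chemistry, and column 17 is Day 15, marked. After Day 18 the marks sit one column too far right. Footnote n fixes the first of these as Days 21, 24 and 27; the last two are Day 31 and EOS.

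**Starting point.** Day -1 is the natural start, because exclusion criterion 6 uses the Day -1 liver values to permit dosing on Day 1.

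**Intervals.** Each is the later day minus the earlier day; there is no Day 0, so Day -1 to Day 2 is 2 days. The stated maximum is 3 days.

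| From | To | Days |
|---|---|---|
| -1 | 2 | 2 |
| 2 | 5 | 3 |
| 5 | 8 | 3 |
| 8 | 11 | 3 |
| 11 | 15 | **4** (dosing) |
| 15 | 18 | 3 |
| 18 | 21 | 3 |
| 21 | 24 | 3 |
| 24 | 27 | 3 |
| 27 | 31 | **4** (after dosing) |

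The maximum is exceeded in 1 of 6 intervals from Day -1 to Day 18, and in 2 of 10 from Day -1 to Day 31. The liver-enzyme sentence covers the whole study. Read literally, it is also missed from Day -8 to Day -1 (7 days, in the unit but before any dose) and from Day 31 to EOS (43 ± 2 - 31 = 10 to 14 days).

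**Robustness.** If the Day 15 mark really belonged to Day 14, the intervals around it would be 11 to 14 = 3 and 14 to 18 = 4. Days 11 and 18 are 7 days apart, so one draw between them always leaves an interval of at least 4 days.

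**What a Day 14 draw would gain.** Take an abnormality that first appears after Day 11 and is present by Day 14. Assume draws are 0.5 h before dosing; laboratory turnaround is not stated, so it is varied.

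| Turnaround | Doses stoppable now | With a Day 14 draw | Gain |
|---|---|---|---|
| 0.25 h | 15 | 14 and 15 | 1 |
| 2 to 24 h | none | 15 | 1 |
| 25 h or more | none | none | 0 |

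The gain is 0 or 1 of 15 doses, at most 1/15 = 6.7%.

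**Schedule after the fix.** Adding Day 14 and keeping Days 15 and 18 gives 2, 3, 3, 3, 3, 1, 3 from Day -1 to Day 18 (0 of 7 above 3 days), then 3, 3, 3, 4 to Day 31. Adding Day 30 as well gives 2, 3, 3, 3, 3, 1, 3, 3, 3, 3, 3, 1 (0 of 12 above 3 days). Moving Day 15 to Day 14, without adding a draw, gives 2, 3, 3, 3, 3, 4, 3, 3, 3, 4: still 2 of 10.

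**The case against.** The strongest reply is that this is a one-day slip with little clinical weight. Even a compliant Day 14 draw would leave doses 12 and 13 uninformed, as every 3-day interval does for the doses inside it, and with slow turnaround it would change nothing. Protocol Table 3 reports transaminase elevations usually after 3 to 6 weeks, later than a 15-day course. Participants stay in the unit until Day 31, abnormal values are repeated, and Day 14 already has a PK/PD draw and, in SAP Table 3, a vital-signs visit. Section 6.6 itself obliges the site to monitor at that interval, and Section 10.2 lets the Investigator order a Day 14 test without departing from the schedule.

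Most of this stands, and it limits the size of the point. The intervals before dosing and after discharge cannot affect a dosing decision, so 1 of 6 is the count that matters. The conflict itself remains: a permitted test is not a scheduled one, and neither vital signs nor PD samples replace ALT or a blood count. The 3-to-6-week timing concerns transaminases only, and Section 6.6 says liver enzyme elevations were occasionally seen in single-dose healthy-volunteer studies.

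**Conclusion.** The concern holds. The schedule leaves one 4-day interval during dosing against a stated maximum of 3 days, and a second 4-day interval after dosing that is of little consequence. It should be corrected because a stated safety commitment and its schedule disagree. It does not show that the study is unsafe, and no endpoint is affected.

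The conclusion rests on the chemistry, hematology and coagulation row alone. The rows of Table 1 after urinalysis are not visible in the copy read, and the late columns are displaced, but the 4-day gap between Days 11 and 18 survives either alignment. The gain of 0 to 1 dose rests on the assumed draw time and on the unstated turnaround.

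**What to change.** **Schedule.** Add chemistry and hematology tubes to the existing Day 14 pre-dose draw, and keep Days 15 and 18. The overnight fast of at least 10 hours before each dose satisfies the 8-hour rule in Section 8.2.

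**Wording.** In Section 4.2 and in both monitoring sentences of Section 6.6, state the same interval and period: *at least every 3 days from Day -1 through Day 18, at least every 4 days thereafter until discharge on Day 31, then at EOS*. This replaces the whole-study claim, which appears only in the liver-enzyme sentence.

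**Alternatives.** Adding tubes to the existing Day 30 draw as well would support *at least every 3 days from Day -1 to discharge, then at EOS*. If no draw is added, the text should say *at least every 4 days from Day -1 to discharge, then at EOS*, which is true of the current schedule but weakens the commitment. The sponsor and investigator decide which applies.

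**Cost.** Day 14 alone adds about 17 tube sets and no venipuncture; safety-laboratory draws from Day -1 to Day 31 rise from 11 to 12 (1/11 = +9%). Adding Day 30 makes it about 34 sets and 13 draws (2/11 = +18%) and informs no dose. Volume per set is not given; at an assumed 5 to 15 mL, each added set takes that much blood, in a study that already relaxes its hemoglobin rule because of repeated sampling (Section 6.6.1.4). Every option, including text only, needs a protocol amendment, and Section 10.1.1 requires ethics approval before design changes are implemented, so it is best bundled with the next one. Until then the Investigator can order the Day 14 tests under Section 10.2.

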### **6.6.1. Adverse Reaction Rules**

An adverse reaction is any treatment emergent adverse event (TEAE) that is considered related to the study medication (for a full definition of related TEAEs, see [Section 10.3.3](#)). When a TEAE occurs, timely determination of relatedness is not always feasible. In such cases, the

Investigator and Alexion should use judgment in protecting the individual patient and study population.

#### **6.6.1.1. General Adverse Reaction Rules**

The general adverse reaction rules refer to all adverse reactions, excluding those relating to the liver and hematology and QT interval prolongation. The Common Terminology Criteria for Adverse Events (CTCAE) may not give clear enough guidance, and grading may not be appropriate for this study in healthy volunteers; therefore, special study-specific rules have been created.

#### **6.6.1.2. Individual Adverse Reaction Rules**

An individual participant will not receive any further dose(s) of ALXN1840, if either of the following occurs:

- Participant experiences any CTCAE Grade 3 (or higher) adverse reaction, or a serious adverse reaction, irrespective of severity/CTCAE grade.
- Participant experiences any CTCAE Grade 1 or 2 adverse reaction considered to be related to ALXN1840 and considered a safety concern by the SRC.

#### **6.6.1.3. Group Adverse Reaction Rules**

Dosing will be suspended for all participants or potentially only in an affected dose group (in the event a dose reduction is employed for the second group), if either of the following occurs:

- One participant experiences a non-serious, severe (CTCAE Grade 3) adverse reaction.
- One participant experiences a serious adverse reaction, irrespective of severity/CTCAE grade.
- One participant experiences a Grade 2 or higher adverse reaction which is considered by the SRC of significant medical consequence to the remaining group to require discontinuation of dosing to the remainder of the group

In the event of suspension of dosing, continuation of the study will require a protocol amendment that has been approved by the MHRA and ethics committee.

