#### **6.6.1.5. Special group Adverse Reaction Rules**

- For special group adverse reaction stopping rules (ie transaminase elevation, hematologic abnormalities and QT prolongation), dosing will be suspended for all participants or to the dosing group if any of the following occurs:
  - One or more participants experience a non-serious, severe (NCI CTCAE Grade 3) or higher adverse reaction.
  - One or more participants experience a serious adverse reaction, irrespective of severity/CTCAE grade
  - One or more participants experience a Grade 2 or higher adverse reaction that is considered by the SRC of significant medical consequence to the remaining group to require discontinuation of dosing to the remainder of the group

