#### **6.6.1.6. Safety Oversight and Implementation Stopping Rules**

- If one or more participants fulfill criteria from either the individual adverse reaction rules (outlined in Section 6.6.1.2 and/or Section 6.6.1.4) or for group adverse reaction rules (outlined in Section 6.6.1.3 and/or Section 6.6.1.5), a SRC meeting will be arranged. At this meeting, a decision will be made regarding the continuation/discontinuation of dosing for the remaining participants as well as need for dose modification. Based on the severity and medical risk to other participants and on request of either the Investigator or Alexion, dosing for all participants will be temporarily suspended until the SRC meets.
- The SRC will meet following completion of Day 18 of Group 1 to confirm adequate safety to complete dosing at 30 mg/day. Dose reduction to 15 mg/day may be made

following review of Group 1 data if there is evidence of over-decuppering as determined by AEs and/or ceruloplasmin concentration.

- The SRC will be comprised of, at minimum, the Investigator and Alexion's Medical Monitor. Additional site staff and Alexion personnel may also be included and will be responsible for reviewing all safety data and making determination around dosing.
- In the event of suspension of dosing, continuation of the study will require a protocol amendment that has been approved by the MHRA and ethics committee.

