6. Other situations: 
 
• Medical or scientific judgment should be exercised in deciding whether SAE reporting is appropriate in other situations such as important medical events that may not be immediately life-threatening or result in death or hospitalization but may jeopardize the participant or may require medical or surgical intervention to prevent one of the other outcomes listed in the above definition. These events should usually be considered serious.
 
• Examples of such events include invasive or malignant cancers, intensive treatment in an emergency room or at home for allergic bronchospasm, blood dyscrasias or convulsions that do not result in hospitalization, or development of drug dependency or drug abuse.
 

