### 10.3.3. Recording and Follow-Up of AE and/or SAE

Recording of AE and/or SAE

 
• When an AE/SAE occurs, it is the responsibility of the Investigator to review all documentation (eg, hospital progress notes, laboratory reports, and diagnostics reports) related to the event.
 
• The Investigator will then record all relevant AE/SAE information in the CRF.
 
• It is not acceptable for the Investigator to send photocopies of the participant’s medical records to Alexion in lieu of completion of the /AE/SAE CRF page.
 
• There may be instances when copies of medical records for certain cases are requested by Alexion. In this case, all participant identifiers, with the exception of the subject number, will be redacted on the copies of the medical records before submission to Alexion.
 
• The Investigator will attempt to establish a diagnosis of the event based on signs, symptoms, and/or other clinical information. Whenever possible, the diagnosis (not the individual signs/symptoms) will be documented as the AE/SAE.
 

Assessment of Intensity
The Investigator will make an assessment of intensity for each AE and SAE reported during the study and assign it to one of the following categories from National Cancer Institute CTCAE v 5.0, published 27 Nov 2017: 
 
• Grade 1: Mild (awareness of sign or symptom, but easily tolerated)
 
• Grade 2: Moderate (discomfort sufficient to cause interference with normal activities)
 
• Grade 3: Severe (incapacitating, with inability to perform normal activities)
 
• Grade 4: Life-threatening
 
• Grade 5: Fatal
 

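### The general group stopping rule names CTCAE Grade 3 without *or higher*, so a Grade 4 reaction classed as non-serious does not automatically suspend the group

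*Protocol*

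**What the plan says.** Protocol Section 6.6.1 sets stopping rules in two families. The general rules apply to all adverse reactions, "excluding those relating to the liver and hematology and QT interval prolongation" (6.6.1.1). The special rules apply to those three areas. Each family has an individual rule and a group rule.

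- **General individual rule (6.6.1.2):** dosing ends for a participant if "Participant experiences any CTCAE Grade 3 (or higher) adverse reaction", or if the reaction is serious. A lower-grade related reaction that the SRC considers a safety concern also counts.
- **General group rule (6.6.1.3):** bullet 1 is "One participant experiences a non-serious, severe (CTCAE Grade 3) adverse reaction". Bullet 2 is "One participant experiences a serious adverse reaction, irrespective of severity/CTCAE grade". Bullet 3 covers Grade 2 and above, but only if the SRC judges the reaction important enough for the rest of the group.
- **Special group rule (6.6.1.5):** the first trigger is "One or more participants experience a non-serious, severe (NCI CTCAE Grade 3) or higher adverse reaction". The other two match bullets 2 and 3 above.
- **Oversight (6.6.1.6):** when any individual or group rule is met, an SRC meeting is arranged. Before it, depending on severity and risk, "on request of either the Investigator or Alexion, dosing for all participants will be temporarily suspended until the SRC meets".

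After a suspension, the study may continue only under a protocol amendment approved by the MHRA and the ethics committee (6.6.1.3 and 6.6.1.6).

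**The concern.** Bullet 1 of 6.6.1.3 stops at Grade 3, whereas 6.6.1.2, 6.6.1.5 and bullet 3 of the same list all extend upward. The protocol writes *or higher* where it means it, so staff applying bullet 1 cannot safely assume that Grade 4 is included. The special group rule does not fill the gap, because the general rules cover everything outside liver, hematology and QT.

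The result is a reversed order in one situation: the milder non-serious reaction suspends everyone automatically and the more severe one does not. There is also a procedural consequence. Automatic suspension brings the requirement for an approved amendment before the study continues. Without it, an SRC that may consist of only the Investigator and the sponsor's medical monitor can decide that the other participants continue. The protocol describes this as the first repeat-dose study of the drug in healthy people, so the stopping thresholds should not depend on inferring a missing phrase.

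**Working it through.** The plan gives no figure to reproduce. The check compares the rules over every combination of grade and seriousness.

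**Inputs.** CTCAE Grades 1 to 5 (10.3.3); serious or not (10.3.2); triggers from 6.6.1.2, 6.6.1.3 and 6.6.1.5. *Automatic* here means a trigger that needs no SRC judgment, so bullet 3 and its counterpart in 6.6.1.5 are set aside.

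**Rules as written.**

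- General group, 6.6.1.3: serious, or grade = 3.
- Special group, 6.6.1.5: serious, or grade ≥ 3.
- General individual, 6.6.1.2: serious, or grade ≥ 3.

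**Cells.** 5 grades × 2 seriousness classes = 10. Non-serious Grade 5 cannot occur, because death is an SAE criterion. That leaves 10 − 1 = 9.

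| Reaction | Individual stop (6.6.1.2) | Automatic group suspension, 6.6.1.3 as written | Automatic group suspension, 6.6.1.5 |
|---|---|---|---|
| Non-serious, Grade 1 | no | no | no |
| Non-serious, Grade 2 | no | no | no |
| Non-serious, Grade 3 | yes | yes | yes |
| Non-serious, Grade 4 | yes | **no** | **yes** |
| Serious, Grades 1 to 5 (five cells) | yes | yes | yes |

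The two group rules differ in 1 of 9 cells: non-serious Grade 4. With *or higher* added to bullet 1, the general rule becomes serious or grade ≥ 3, and the two group rules agree in all 9 cells.

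**Can the cell occur?** The protocol gives "Grade 4: Life-threatening" as the intensity category (10.3.3), and life-threatening is also an SAE criterion (10.3.2). Most Grade 4 reactions would therefore be serious and fall under bullet 2. The two assessments are nevertheless separate. The SAE criterion requires that the participant was actually in danger of dying when the event occurred, and it excludes events that could only hypothetically have been fatal. A Grade 4 event that does not meet this, or another SAE criterion such as hospitalization, is left to the category of other important medical events, for which the protocol says "These events should usually be considered serious". That is guidance, not a requirement. Section 6.6.1.5 itself provides for non-serious reactions above Grade 3.

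**What still happens in that cell.** The affected participant stops (6.6.1.2). An SRC meeting is arranged and decides on dosing for the others (6.6.1.6). Suspension before the meeting depends on a request (6.6.1.6), and suspension under bullet 3 depends on SRC judgment (6.6.1.3). Neither is automatic.

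**The case against.** The strongest objection is that the cell has almost no content. The protocol defines Grade 4 as life-threatening, and an event so graded would naturally be judged under the SAE criterion of the same name, which has no qualifier. The softer wording belongs to a different SAE category, meant for events that may not be immediately life-threatening. A laboratory example, such as a very high creatine kinase (in the Section 10.2 panel and outside the liver and hematology rules), needs several steps. The value must be judged clinically significant to be an AE, considered related to be an adverse reaction, graded 4, and still classed as non-serious. The documents give no CTCAE cut-offs for that test, and the laboratory grading in Section 9.4.2 serves summary tables.

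The comparison is also imperfect. The individual rule has no non-serious limiter, and the special rules deal with findings for which the protocol ties grade to numeric limits, so a high grade without clinical seriousness is more plausible there. Other safeguards apply: the sponsor must be told within 24 hours of any AE of clinical concern (6.6), and both parties are told to use judgment to protect the study population when relatedness cannot be settled promptly (6.6.1). Finally, 1 of 9 cells is a count of rule outcomes, not a probability.

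Much of this stands. The case is rare, the backstops are real, and the cell count says nothing about frequency. It does not remove the point. The SAE criterion is narrower than the Grade 4 label, so a non-serious Grade 4 reaction is possible. The safeguards rest on a request or a judgment, so they do not restore the automatic trigger or the external approval that follows from it. Nothing in the documents suggests that Grade 4 was left out on purpose.

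**Conclusion.** The concern holds as a minor error in a safety threshold. As written, 6.6.1.3 does not automatically suspend the group for a general Grade 4 reaction classed as non-serious, although it does for a non-serious Grade 3 reaction. The discrepancy is confined to 1 of 9 feasible cells.

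The conclusion rests on a literal reading of bullet 1 and on grade and seriousness being assigned separately. Confidence in the textual mismatch is high. The practical consequence is small, given the overlap between Grade 4 and seriousness, the mandatory SRC meeting, and a sample of about 17 healthy participants. No endpoint, analysis set or estimate is affected.

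**What to change.** In bullet 1 of Section 6.6.1.3, insert *or higher* after the bracketed grade, so that the trigger is a non-serious reaction of CTCAE Grade 3 or above, as in 6.6.1.5. Bullets 2 and 3 and Section 6.6.1.6 can stay as they are.

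The cost is one phrase in the next protocol amendment, with no effect on data collection or analysis. The change can only add protection.
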